5.2. Determination of Sample Size

The study is planned to have a minimum of approximately 162 patients randomized 1:1 to placebo or galcanezumab 300 mg with the opportunity to increase the final sample size at an interim analysis if indicated in order to maintain a well powered study. To preserve blinding, details of the sample size and power calculations are omitted from this SAP and are provided in a separate document to the Ethical Review Board (ERB).

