5.5.1.4. Multiple Comparisons/Multiplicity

The primary efficacy analysis will be the overall treatment effect of galcanezumab 300 mg every 30 days vs. placebo using a MMRM analysis, which is equivalent to the average of the MMRM-estimated weekly treatment effect over the 12-week double-blind treatment phase for change in weekly cluster headache attack frequency from baseline. The Type I error rate will be controlled at a 1-sided 0.025 level for the primary efficacy analysis.

A fixed sequential gatekeeper method will be utilized for testing secondary hypotheses to be eligible for inclusion in the proposed label. Specific details of the testing of the secondary gatekeeper objectives are provided in Section [5.5.8.2](#).

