If necessary, both the default and the scoring fitting algorithms will be used in the pre-specified order before proceeding to the next covariance structure in the sequence. For models where the unstructured covariance matrix is not utilized, the sandwich estimator (Diggle et al. 1994) will be used to estimate the standard errors of the fixed effects parameters. The sandwich estimator is implemented by specifying the EMPIRICAL option in SAS®. When the sandwich estimator is utilized, the Kenward-Roger approximation for denominator degrees of freedom cannot be used. Instead, the denominator degrees of freedom will be partitioned into between-subject and within-subject portions by the DDFM=BETWITHIN option in SAS®. SAS® PROC MIXED will be used to perform the analysis.

If the sample size is not increased, a conventional analysis based on the single contrast with MMRM as specified above will be conducted. If the sample size is increased as a result of the interim analysis, the Cui, Hung, and Wang (CHW) procedure (Cui et al. 1999) will be applied to the primary endpoint to control the Type I error at a one sided $\alpha=0.025$ significance level. The CHW method ensures strong control of Type I error when the sample size is increased in a data dependent manner. The detailed approach to control Type I error using CHW procedure is described in [Appendix 1](#).

If the sample size is increased as a result of the interim analysis, an unadjusted point estimate for the primary efficacy analysis will be calculated and reported. A median unbiased point estimate and a stage-wise adjusted confidence interval for the primary efficacy analysis will be calculated and reported based on the approach described in Brannath et al. 2009 to assess sensitivity of the point estimate.

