5.5.11. Sensitivity Analysis

Dynamic Allocation (Minimization) Assumption

A permutation test will be performed as a sensitivity analysis of the primary MMRM analysis to confirm the results of the asymptotic inference. The key features of the permutation test which will be employed are as follows:

- The patients' baseline covariates, responses, and enrollment order will be considered fixed.
- The sharp null hypothesis will be assumed (that is, responses to GMB and placebo will be assumed exactly equal).
- The exact minimization algorithm and exact site pooling algorithm will be used to generate the null distribution of the primary test statistic from the MMRM analysis.
- The p-value based on the generated null distribution (that is, permutation test p-value) will be obtained by comparing the observed test statistic value to the percentiles of the generated null distribution.

Explicitly, the p-value is derived from the permuted distribution of test statistics as follows. If the total number of permutations is m , and b of these permutations have a test statistic greater than or equal to the observed test statistic, z , then the permutation p-value, p^p is,

$$p^p = \frac{b + 1}{m + 1}$$

where m equals 100,000. As discussed in Phipson and Smith 2010, this is an upper bound on the estimated p-value. This method is used to generate the approximate null distribution. Note that the described permutation p-value calculation should be conducted such that a positive value for the test statistic should indicate a favorable treatment effect GMB 300 mg relative to placebo.

If the sample size is not increased based on the interim results, the permutation test will be performed on the combined data from the interim and post-interim assessments since the CHW procedure will not be applied. If the sample size is increased, then the permutation test will be

performed on patients before and after the interim analysis. These results will be combined using the CHW procedure. The details of computing CHW statistics for the permutation test is summarized in [Appendix 1](#).

Missing Data Assumption

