Sensitivity analyses will be performed to assess the robustness of the primary analysis conclusions to deviations from MAR assumption. The approach for these analyses is to vary the assumptions of missing data for the primary analysis in a systematic way. Basically, the method will be to predict the missing outcomes and then add a value (denoted as Δ_A) to the predictions in the active treatment group and another value (denoted as Δ_P) to the predictions in the placebo treatment group, consistent with the sensitivity approach suggested in Permutt (2015). This procedure will be repeated multiple times for different values of (Δ_A, Δ_P) using the following steps:

1. Predict the missing outcomes for each treatment via multiple imputation based on observed primary endpoint and baseline values. Such imputation will be carried out using a Markov Chain Monte Carlo method with a Jeffreys prior via SAS® PROC MI. Thirty (30) such imputations will be created.
2. Add Δ_A to the imputed values for patients taking active treatment and Δ_P to the imputed values for patients taking placebo.
3. Conduct the primary analysis separately for each of the 30 imputations.
4. Combine the results of these analyses using Rubin's combining rules, as implemented in SAS® PROC MI ANALYZE.

The above steps will be repeated multiple times for different values of (Δ_A, Δ_P) with Δ_P ranging from (0, twice the absolute value of the mean value seen for placebo in the primary analysis) and Δ_A ranging from $(\Delta_P, \Delta_P + \text{absolute value of the mean treatment difference seen within the primary analysis})$. For example, if the mean change from baseline for placebo is -3.6 and the corresponding treatment difference is -1.5, then Δ_P would range from (0, 7.2) and Δ_A would range from $(\Delta_P, \Delta_P + 1.5)$.

Normality Assumption

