To assess the robustness of the MMRM results to deviations from normality assumption, a sensitivity analysis for raw number of cluster headache attacks (total number of cluster headache attacks for each interval without imputing missing value and without normalization to 14-day period) will be conducted with a repeated measures negative binomial regression model fitted with SAS® PROC GLIMMIX. The model will include treatment, gender, pooled investigative site, bi-weekly time period (Weeks 1/2, 3/4, etc.), baseline verapamil use (yes or no) and treatment-by-time-period interaction, as well as the continuous fixed covariates of baseline value, and log (number of compliant days within each bi-weekly time period divided by 14) as the offset in the model. In case of non-convergence, pooled investigative site may be excluded from the model. Directional consistency of treatment effects from this model and the primary analysis MMRM model as specified in Section [5.5.8.1](#) will be examined.

In addition, as another form of sensitivity analysis, residuals from the primary analysis MMRM model will be examined and outliers identified. Consistency of results before and after removing patients with outlier residuals will be examined.

All sensitivity analyses discussed above will be using ITT population including pre- and post-interim 1 data.

Pre- and Post-interim Consistency Assessment

If the sample size is increased based on the interim analysis data, differences between pre and post interim 1 data for baseline variables and endpoints will be evaluated. Specifically, baseline patient characteristics as summarized in Section 5.5.4 will be summarized for pre and post interim data separately. In addition, change from baseline in weekly cluster headache attacks frequency using all pre and post interim 1 data combined will be analyzed with MMRM method as specified in Section 5.5.8.1 with the exception of adding a binary covariate of “pre and post interim 1 status” with value of 1 for pre interim 1 data, and value of 0 for post interim 1 data, and pre and post interim 1 status-by-treatment interaction.

CCI

CCI

[REDACTED]

[REDACTED]

[REDACTED]

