Appendix 1. Calculation of CHW Statistics

Calculation of the CHW Statistics for Primary Analysis

As pointed out by Mehta and Pocock (2010), regardless of the rule for increasing the sample size following interim analysis, if the conventional Wald statistic is replaced by the CHW statistic, then the Type I error is preserved (Cui et al. 1999). This section describes the approach to calculating the CHW statistic using the primary MMRM analysis results.

Table APP1.1. Defining the Quantities for the CHW Test Statistic

Quantity	Input Value or Derivation/Calculation
z_1	This is the associated test statistic for the LSMean difference of LY2951742 (300 mg) versus placebo for the primary efficacy analysis conducted using only patients included in the interim assessment . The LSMean contrast should be conducted such that a positive value for the test statistic should indicate a favorable treatment effect LY2951742 (300 mg) relative to placebo, that is LSMean for placebo – LSMean for LY2951742 (300 mg).
z_2	This is the associated test statistic for the LSMean difference of LY2951742 (300 mg) versus placebo for the primary efficacy analysis conducted using only the set of patients included in the post-interim assessment . The LSMean contrast should be conducted such that a positive value for the test statistic should indicate a favorable treatment effect LY2951742 (300 mg) relative to placebo, that is LSMean for placebo – LSMean for LY2951742 (300 mg).
n_1	This is the pre-specified total number of randomized patients included in the interim analysis for both the LY2951742 (300 mg) treatment group and the placebo treatment group. These are patients randomized on or before the randomization cutoff date who had the opportunity to complete the trial, regardless of whether they provided postbaseline data to the interim analysis. The interim is scheduled to occur when 70% of randomized patients have had the opportunity to complete the treatment phase at $n_1 = 114$.
n_2	This is the pre-specified planned increment from n_1 for the total number of patients in both the LY2951742 (300 mg) and placebo treatment groups should the study remain at the planned minimum sample size based on interim results. The planned minimum sample size is 162 and if the interim occurs at the planned $n_1 = 114$, the increment needed to get to 162 patients is $n_2 = 48$.

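### If the sample size is increased, the delta-adjusted missing-data analysis has no CHW step, so it tests a different statistic from the one that decides the trial

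*SAP*

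**What the plan says.** **Deciding test.** SAP 5.5.1.4 sets the standard: "The Type I error rate will be controlled at a 1-sided 0.025 level for the primary efficacy analysis". Under 5.5.8.1, if the sample size is increased, CHW "will be applied to the primary endpoint to control the Type I error at a one sided" 0.025 level. Without an increase, a conventional repeated-measures (MMRM) contrast is used. Appendix 1, Table APP1.1, fixes the CHW weights from n1 = 114 and n2 = 48.

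**Permutation test.** SAP 5.5.11 has a separate branch for an increased sample size: the test is run on patients before and after the interim, and "These results will be combined using the CHW procedure". Table APP1.2 gives the formulas.

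**Delta-adjusted missing-data analysis.** This part of 5.5.11 is meant to show whether the primary conclusions survive departures from missing at random. It imputes 30 times, adds deltas by arm, then says: "Conduct the primary analysis separately for each of the 30 imputations". Step 4 combines the results by Rubin's rules. There is no branch for an increased sample size, no split by stage and no mention of CHW. Appendix 1 does not cover it.

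**Data used.** The section later states: "All sensitivity analyses discussed above will be using ITT population including pre- and post-interim 1 data".

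**Size.** SAP 5.2 says: "The study is planned to have a minimum of approximately 162 patients randomized 1:1 to placebo or galcanezumab 300 mg". It adds that "details of the sample size and power calculations are omitted from this SAP". SAP 5.6 places the details of the first interim analysis in the Statistical Analysis Center SAP, the ERB supplement and the DMC Charter.

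**The concern.** After an increase, the conclusion to be stress-tested is that the CHW statistic exceeds 1.96. CHW gives the interim patients 70.4% of the squared weight and the later patients 29.6%, whatever the final size. A pooled MMRM weights the stages by the information they actually contribute, so the later patients count for more than 29.6%.

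A delta analysis built on the pooled fit therefore starts from a different z-value. It could fail with no delta applied although the primary test succeeded, or show a margin that the deciding test does not have. In neither case would it show where the primary conclusion breaks. Leaving the text open also leaves a choice between two tests to be made after the results are known.

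**Working it through.** **Inputs from the SAP.** One-sided alpha 0.025 (5.5.1.4), so the critical value is 1.96. Minimum N = 162 (5.2). Interim timing (Appendix 1): "The interim is scheduled to occur when 70% of randomized patients have had the opportunity to complete the treatment phase", with n1 = 114 and n2 = 48.

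**Assumed, because the documents do not give them.** Increased totals N\* of 180, 200, 243 and 324; an interim z of 1.70; information proportional to patient numbers; illustrative increase rules.

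**Step 1: reproduce the SAP's figures.** 0.70 × 162 = 113.4, rounded up to 114; 162 − 114 = 48. The weights are √(114/162) = 0.8389 and √(48/162) = 0.5443, with squares 0.704 and 0.296. Numerical integration under the null gives a CHW rejection probability of 0.0250, as intended.

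**Step 2: the two statistics.**
- z_CHW = 0.8389 z1 + 0.5443 z2
- z_pool = √(114/N\*) z1 + √((N\* − 114)/N\*) z2

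At N\* = 243 the second stage has 129 patients (53.1% of the total), and the pooled weights are 0.6849 and 0.7286.

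**Step 3: zero delta, N\* = 243, z1 = 1.70.** If r is the ratio of stage 2 to stage 1 observed effect, z2 = r × 1.70 × √(129/114).

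| r | z2 | z_pool | z_CHW |
|---|---|---|---|
| 1.0 | 1.808 | 0.6849×1.70 + 0.7286×1.808 = 2.482 | 0.8389×1.70 + 0.5443×1.808 = 2.410 |
| 0.6 | 1.085 | 0.6849×1.70 + 0.7286×1.085 = 1.955 | 0.8389×1.70 + 0.5443×1.085 = 2.017 |

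With equal effects, the estimate can shrink proportionally in both stages by 1 − 1.96/2.482 = 21.0% (pooled) or 1 − 1.96/2.410 = 18.7% (CHW) before significance is lost. The pooled breaking point is about 12% further out (21.0/18.7 = 1.12). With r = 0.6 the pooled analysis is not significant and CHW is.

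**Step 4: when each is larger.** z_pool exceeds z_CHW only if r is above a threshold.

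| N\* | 180 | 200 | 243 | 324 |
|---|---|---|---|---|
| Threshold r | 0.92 | 0.87 | 0.79 | 0.69 |
| Excess of z_pool at r = 1 | 0.3% | 1.0% | 3.0% | 6.9% |

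**Step 5: dependence on the increase rule.** One-sided type I error of the pooled test at the four totals:
- N increased only at conditional power 0.5 to 0.9: 0.0242, 0.0236, 0.0225, 0.0213.
- N increased whenever conditional power is below 0.9: 0.0260, 0.0268, 0.0279, 0.0292.
- Least favourable rule: 0.0267, 0.0283, 0.0306, 0.0334.

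**Step 6: disagreement under a true effect.** Simulation with effects of 0.30 to 0.45 SD and totals of 203, 243 or 324. If N is increased in every trial, only the pooled test rejects in 1.4% to 7.9% of trials, and only CHW in 0.3% to 2.5%. If N is increased only at conditional power 0.5 to 0.9, then among the trials increased the figures are 0.0% and 0.7% to 5.8%.

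**The case against.** **Step 3 of the delta analysis names the primary analysis, and 5.5.8.1 includes CHW after an increase.** So CHW may be intended, and pooling is inferred from silence. That is fair, but it does not make the steps executable. Rubin's rules combine estimates and standard errors, whereas CHW produces a z-value from two separate fits. The SAP does not say whether imputation is by stage, or whether Rubin's rules come before or after CHW. The text needs a change on either reading.

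**The sentence on pre- and post-interim data does not prove pooling.** This stands. It also covers the permutation test, which is split by stage and combined by CHW. The evidence is the missing CHW step, not that sentence.

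**A reader might infer that the pooled analysis is the less strict one.** The documents do not support this. Steps 3 to 6 show both directions, and the sign turns on an increase rule held elsewhere.

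**A reader might extend the point to the negative binomial and outlier analyses.** Section 5.5.11 judges the first on direction of effect and the second on consistency after removal, with no significance threshold. CHW would add little there.

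**A sensitivity analysis need not control type I error, and the SAP sets no pass/fail rule for the delta grid.** Both statements are true. The point is about matching the statistic being probed, not about alpha. The SAP's adjusted estimate and its stage-by-treatment interaction model are useful after an increase, but neither applies the deltas to the CHW result.

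**Conclusion.** The gap is real, narrow and minor. If the sample size is increased, the delta-adjusted missing-data analysis as written does not address the CHW statistic on which the primary conclusion rests, although the same section does this for the permutation test. In the worked case the two z-values differ by 0.07 with equal stage effects (2.482 against 2.410). They differ by 0.06 in the other direction (1.955 against 2.017) when the second-stage effect is 0.6 of the first. Differences of this size matter only for a result near 1.96.

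These sizes rest on an assumed total of 243, an assumed interim z of 1.70 and information proportional to patient numbers. The maximum size and increase rule are not in these documents, so no general direction can be claimed. If the sample size is not increased, the issue does not arise.

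**What to change.** Add a branch for an increased sample size to the missing-data part of SAP 5.5.11, settled before the study team is unblinded at the second interim analysis:

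1. Impute, add the deltas, fit the MMRM and apply Rubin's rules separately in the interim and post-interim patients.
2. Convert each combined two-sided p-value to a signed z, positive when galcanezumab is favoured.
3. Combine the two with the Table APP1.1 weights (n1 = 114, n2 = 48).
4. Report the (Δ_A, Δ_P) pairs at which z_CHW falls below 1.96, and keep the pooled delta estimates as descriptive.

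The negative binomial and outlier analyses need no change. The cost is a few sentences in the SAP and repeat runs by stage. The drawback is that imputation models are fitted on smaller samples. The protocol synopsis plans 146 completers of 162, so about 10% do not complete (16/162 = 9.9%), and the smaller stage may contain few missing cases per arm.

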5.6. Interim Analyses

Up to 2 interim analyses may be conducted for Study CGAM. Interim analysis 1 during SP III may be conducted which may result in increasing the sample size or stopping the trial for futility. Details will be documented in the Statistical Analysis Center (SAC) SAP, ERB supplement, and data monitoring committee (DMC) Charter.

The CHW procedure as described in Appendix 1 will be applied to the primary and gated secondary endpoints if the sample size is increased since an increase based on interim results may potentially inflate the type I error.

The IA2 will be conducted after all patients have completed 12 weeks of treatment (SP III) and, thus, will be the final analysis of the primary efficacy endpoint. Interim analysis 2 will be conducted using internal unblinded study team members who do not have direct interaction with sites.

In order to minimize the potential operational and statistical bias that may result from performing an interim analysis, the IA1 for this study will be conducted under the auspices of an independent DMC. The DMC will also independently monitor patient safety during this trial.

Only the DMC is authorized to evaluate unblinded interim efficacy and safety analyses (prior to the completion of the double-blind treatment phase). Study sites will receive information about interim results ONLY if they need to know for the safety of their patients.

5.7. Unblinding Plan

5.7.1. *Unblinding Plan for Interim Analysis 1*

The unblinding plan for IA1 is documented in the SAC SAP.

5.7.2. *Unblinding Plan for Interim Analysis 2*

Interim analysis 2 will be conducted by unblinded study team members who do not have direct interaction with sites. All study personnel with direct interaction with sites are kept blinded to individual patient treatment information.

5.8. Reports to be Generated at Each Interim and Final Database Lock

5.8.1.1. Report to be Generated at Interim 1 Database Lock

The report to be generated at IA1 is described in SAC SAP.

5.8.1.2. Report to be Generated at Interim 2 Database Lock

For the IA2, the database will be locked after all randomized patients have had the chance to complete 12 weeks of treatment in SP III. However, some patients will be still ongoing in SP IV and SP V at the time of the database lock. The last patient visit date of SP III will be used as the data cutoff date for including data for IA2. Any data up to the data cutoff date in the locked database from all study phases will be used, and all analyses specified in this SAP will be performed. However, only analyses conducted for SP III at IA2 will be considered as the final analyses. The analyses using data from SP IV and SP V will be rerun and updated when the completed data are available at the final database lock.

5.8.1.3. Report to be Generated at Final Database Lock

For final database lock, all analyses including tables, figures, and listings that use data from SP IV and SP V will be generated.

5.9. Clinical Trial Registry Analyses

Additional analyses will be performed for the purpose of fulfilling the Clinical Trial Registry (CTR) requirements. These analyses will be the responsibility of the Sponsor.

Analyses provided for the CTR requirements include the following:

A summary of AEs will be provided as a dataset that will be converted to an XML file. Both Serious Adverse Events and ‘Other’ Adverse Events are summarized by treatment group and by MedDRA PT.

- An AE is considered “Serious” whether or not it is a TEAE.
- An AE is considered in the “Other” category if it is both a TEAE and is not serious. For each Serious AE and ‘Other’ AE, for each term and treatment group, the following are provided:
 - the number of participants at risk of an event
 - the number of participants who experienced each event term
 - the number of events experienced.
- Consistent with www.ClinicalTrials.gov requirements, “Other” AEs that occur in fewer than 5% of patients in every treatment group may not be included if a 5% threshold is chosen.
- Adverse event reporting is consistent with other document disclosures for example, the clinical study report [CSR], manuscripts, and so forth.

6. References

Diggle PJ, Liang K-Y, Zeger SL. 1994. Analysis of Longitudinal Data. New York: Oxford University Press.

Guy W. ECDEU assessment manual for psychopharmacology, revised 1976. Rockville, MD: National Institute of Mental Health, Psychopharmacology Research Branch. p 217-222. Available at: <https://archive.org/details/ecdeuassessmentm1933guyw>. Accessed September 29, 2014.

